9.3.4. Safety Analyses

Safety analysis will be based on the safety set.

AEs will be analyzed using quantitative and qualitative measures. AEs will be summarized by treatment group for all AEs, ADEs, SAEs, SADEs (unanticipated SADE (USADE), or anticipated SADE (ASADE)), deaths, AEs leading to discontinuation of dCBT-PF or to withdrawal from investigation, and device deficiencies. AEs will be coded using the Medical Dictionary for Regulatory Activities (MedDRA) and summarized by system organ class and preferred term for each treatment group. ADEs and SADEs only applies to the dCBT-PF therapy group.

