7.1. Discontinuation of Investigational Medical Device treatment

A subject should be discontinued from the dCBT-PF if, in the opinion of the investigator it is medically necessary or if it is the wish of the subject.

If treatment with dCBT-PF is discontinued, the investigator or designee should make all efforts to ensure that the subject will remain in the clinical investigation and ensure that the subject attends the remaining visits.

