8.4. Adverse Events, Serious Adverse Events, and Other Safety Reporting

The definitions and reporting requirements for AEs, ADEs, SAEs, and SADEs can be found in Appendix 2 (see Section 10.2).

AEs will be reported by the subject and will be classified as AEs, ADEs, SAEs, and SADEs according to the definitions provided in Section 10.2. ADEs and SADEs can only occur in the dCBT-PF group as there are no intervention in the control group. All ADEs, SAEs and SADEs should be reported in the CRF. Aes, not fulfilling the definition of an ADE, SAE, and SADE, should only be reported if they are related to a psychological disorder or a procedure of the clinical investigation.

The investigator and any qualified designees are responsible for detecting, documenting, and recording events that meet the definition of an AE, ADE, SAE, or SADE. They further remain responsible for following up on AEs, ADEs, SAEs, or SADEs.

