8.4.1. Time Period and Frequency for Collecting AE and SAE Information

AEs, ADEs, SAEs and SADEs will be collected from signing of the ICF at baseline (V1) and until Week 4 (pilot phase) or Week 12 (pivotal phase), respectively, at the timepoints specified in the SoA (see Section 1.3). Aes, ADEs, SAEs and SADEs are followed until they have reached a final outcome or the subject's participation in the clinical investigation ends, whichever comes first.

All SAEs and SADEs will be recorded and reported to the sponsor immediately and under no circumstance should this exceed 24 hours after SAE / SADE awareness. The investigator or designee will submit any updated SAE/SADE data to the sponsor within 48 hours of it being available. For all reportable events, the sponsor will adhere to local reporting timelines.

Information on relevant AEs, ADEs, SAEs, and SADEs must be entered in the CRF.

Investigators are not obligated to actively seek information on AEs, ADEs, SAEs, or SADEs after conclusion of the clinical investigation participation. However, if the investigator learns of any SAE or SADE, including a death, at any time after a subject has been discharged from the clinical investigation, and he/she considers the event to be reasonably related to the intervention or participation in the clinical investigation, the investigator must promptly notify the sponsor regardless of the time that has elapsed (post-clinical investigation events).

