9.3.5. Other Analyses

The subject flow including total number of screened subjects, number of randomised subjects, completers, withdrawn subjects (including reason for withdrawal) and subjects included in each of the analysis sets will be summarized by group and for the total.

Health care utilisation will be summarized by type of health care utilisation and by treatment group.

The number of subjects with major deviations will be summarized by category of violation and by treatment group.

Adherence to the device will be summarized using descriptive statistics for the subjects randomised to dCBT-PF.

Demographic and baseline characteristics will be summarized using descriptive statistics for each treatment group and for the total number of randomised subjects. Medical history will be coded using MedDRA and summarized by system organ class and preferred term for each treatment group. Prior medications will denote medications used prior to first dose of

investigational medical device independent and stopped at latest at randomization. Concomitant therapy will denote medications started prior to but continuing after randomization or medications with a start date at or after the randomization date. Prior and concomitant therapy will be summarized separately by Anatomical Therapeutic Chemical levels 2 and 4.

Subgroup analyses of the primary and key secondary endpoints will be made to assess consistency of the intervention effect across at least the following subgroups:

[figure not shown]
- Age group: $<65 \text{ vs} \ge 65 \text{ years}$
- Sex: female vs male
- Baseline disease severity (GAD-7 score at baseline: 5-9, 10-14, ≥15)

If the number of subjects is too small (less than 10%) within a subgroup, then the subgroup categories may be redefined prior to data analysis. Further details on the statistical analysis will be provided in a statistical analysis plan.

Answers to functionality interview of the DTx will be evaluated using qualitative methods and will be reported separately.

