10.2.5. Recording and follow-up on of AE, ADEs, SAEs or SADEs

AE, ADE, SAE, SADE and device deficiency recording

- AEs/ADEs/SAEs/SADEs will be collected from signing the ICF. Device deficiencies will be collected from start of dCBT-PF use.
- A pre-existing medical condition should be reported if the condition increases in severity (e.g. from non-severe to severe).
- At each visit the subject should be asked about AEs in an objective manner, e.g.: "Have you experienced any problems since the last visit?".
- All AEs/ADEs/SAEs/SADEs should be followed until they have reached a final outcome (Resolved, resolved with sequelae, death) or the subject's participation in the trial ends, whichever comes first.
- The outcome "Ongoing" can be used as the final outcome for events that are not expected
 to resolve over time.
- ADEs, SADEs should be followed on a regular basis according to the investigator's clinical judgment until a final outcome has been established.

Causality of AEs (relationship to device or procedure)

- Not related
- Possible
- Probable
- Causal

The AEs fulfilling causality criteria possible, probable and casual are all classified as ADEs

Event status

The Investigator is obliged to record the most appropriate outcome using the following categories:

- Resolved
- Resolved with sequelae
- Ongoing
- Death

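### The 9.3.4 summary of AEs that end dCBT-PF use or participation is incomplete by rule, because 8.4 and 10.2.1 leave new, non-serious, unrelated physical illness unreported even when it is why a subject stopped

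*Combined protocol and SAP*

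**What the plan says.** **The planned output.** Section 9.3.4 lists, among the AE summaries by treatment group, "AEs leading to discontinuation of dCBT-PF or to withdrawal from investigation". The row is not restricted to any type of AE.

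**What is reported.** Section 8.4 states that "All ADEs, SAEs and SADEs should be reported in the CRF". Any other AE "should only be reported if they are related to a psychological disorder or a procedure of the clinical investigation". Section 10.2.1 repeats the restriction. Section 8.4.1 adds that "Information on relevant AEs, ADEs, SAEs, and SADEs must be entered in the CRF", without defining which AEs are relevant.

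**How an event becomes an ADE.** Under 10.2.5, "The AEs fulfilling causality criteria possible, probable and casual are all classified as ADEs". Under 8.4, "ADEs and SADEs can only occur in the dCBT-PF group as there are no intervention in the control group".

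**Why subjects may stop.** Section 7.1 provides for stopping dCBT-PF if "in the opinion of the investigator it is medically necessary or if it is the wish of the subject". It does not confine this to serious or psychological events.

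**Related records.** Section 9.3.5 summarizes reasons for withdrawal as part of subject flow. Section 7.1.1 asks for the reason for a temporary stop in the CRF; 7.1 has no matching requirement for a permanent stop. Section 10.2.5 also says that a pre-existing condition should be reported when it becomes more severe.

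**The concern.** A row on AEs that end treatment or participation is a usual tolerability summary, and readers will take it to cover all such AEs. Here the reporting rule was written for a narrower purpose and does not mention events that end treatment or participation. Section 2.2 describes patients with PF as often susceptible to lung infections, so a non-serious infection judged unrelated to the app is a plausible reason to stop daily use or to leave. Under the rule, that subject can appear as a discontinuation or withdrawal with no associated AE. What is at stake is whether a descriptive safety table is complete and whether its two columns can be compared.

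**Working it through.** No arithmetic applies: the plan gives no figure for this row and none for expected withdrawals. The check compares what the row needs (every AE that led a subject to stop dCBT-PF or to leave) with what may be reported.

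| AE that ends treatment or participation | dCBT-PF arm | Control arm | Source |
|---|---|---|---|
| Serious | Reported | Reported | 8.4, 10.2.3 |
| Non-serious, psychological | Reported | Reported | 8.4, 10.2.1 |
| Non-serious, procedure-related | Reported | Reported | 8.4, 10.2.1 |
| Non-serious physical, at least possibly device-related | Reported as ADE | Route does not exist | 8.4, 10.2.5 |
| Non-serious worsening of a pre-existing condition, unrelated | Depends on whether 10.2.5 or 8.4 governs | Same | 8.4, 10.2.1, 10.2.5 |
| New, non-serious physical illness, unrelated | Not reported | Not reported | 8.4, 10.2.1 |

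1. *Could such an event enter as an SAE?* No. The criteria in 10.2.3 cover death, serious deterioration in health and foetal events. Causing discontinuation is not among them.
2. *Could it enter as an ADE?* Only with a causality rating of possible or higher, and only in the dCBT-PF arm.
3. *Does 10.2.5 close the gap?* If its sentence on worsened pre-existing conditions overrides the restriction, non-serious worsening of PF or of an existing comorbidity is captured, but new unrelated illness is still left out. If the restriction governs, both are left out. The text does not settle which applies.
4. *Is the omitted set empty?* No. A first respiratory infection that is non-serious and judged unrelated, after which the subject stops the app or leaves, falls in the last line of the table.
5. *Effect by arm.* Stopping the app can occur only in the dCBT-PF group, so the comparison between arms concerns withdrawal. A non-serious physical illness followed by withdrawal can enter the row in the dCBT-PF arm if rated possible; a like event in a control subject has no such route. The count is understated in both arms, and the comparison, if distorted by this route, is tilted against the device.

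**The case against.** Selective AE collection looks deliberate. Section 2.3.1 names negative wellbeing or distress as the residual risk and expects no other to cause ADEs. The omitted events are by definition non-serious and judged unrelated, so they say little about device harm. The one event type for which 7.2 requires withdrawal, significant new or worsened distress, is psychological and is captured. The row could be read as meaning reportable AEs, and a footnote would then remove the mismatch. This argument stands as far as it goes and limits the importance of the point. It does not make the row, as now labelled, complete.

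Several stronger readings are tempting, but the documents do not support them:

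- *That the plan forbids recording these events.* Section 8.4 also makes investigators responsible for recording events that meet the AE definition. The restriction is on reporting.
- *That the row cannot be filled.* Four of the six lines in the table above feed it in the dCBT-PF arm and three in control.
- *That the row must contradict the reasons for withdrawal in 9.3.5.* The categories for that field are not given, and disposition and coded AEs are different measures. They may differ; the text does not show that they must.
- *That the gap undermines the missing-at-random assumption or the primary result.* Subjects who stop the app are to remain and attend later visits (7.1), and the estimand follows treatment policy. Reasons for withdrawal are still summarized. The imputation in 9.3.2 uses baseline characteristics, treatment and GAD-7 scores, not AE records, and sensitivity analyses with opposite-group imputation and a tipping point are planned.
- *That a number of missing subjects can be stated.* The documents give neither a withdrawal rate nor the share due to such illness, and 250 is a maximum enrolment.

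Section 9 defers detail to a SAP. A SAP could relabel the row, but it could not restore events that were never reported.

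**Conclusion.** The mismatch is real and can be shown from the text alone. Following 8.4 and 10.2.1 leaves the 9.3.4 row without new, non-serious physical illness judged unrelated to device and procedure, in both arms, and the ADE route makes the row potentially uneven between arms. This assumes that sites follow the reporting restriction as written and that the row is built from reported AEs. The gap is wider if 10.2.5 does not override the restriction. Its size in subjects is unknown. The consequence is confined to a descriptive safety summary, so this is a data-capture correction of modest importance.

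**What to change.** Add one sentence to 8.4 and to 10.2.1: any AE that causes a subject to stop dCBT-PF, temporarily or permanently, or to leave the investigation is reported in either arm, whatever its nature, seriousness or causality. Link that AE record to the reason-for-withdrawal field so that the 9.3.4 and 9.3.5 tables can be checked against each other. Reconcile the 10.2.5 sentence on worsened pre-existing conditions with 8.4 and 10.2.1, and define which AEs count as relevant in 8.4.1.

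If AE collection is to stay as it is, label the 9.3.4 row as limited to reportable AEs and cross-refer to the reasons for withdrawal in 9.3.5.

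The cost of the full change is a few more AE forms and a slightly higher reported count of AEs that end treatment or participation. It changes what is captured, not how subjects are managed. It is best made before subjects leave, since the detail may be hard to recover afterwards.

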9.3.5. Other Analyses

The subject flow including total number of screened subjects, number of randomised subjects, completers, withdrawn subjects (including reason for withdrawal) and subjects included in each of the analysis sets will be summarized by group and for the total.

Health care utilisation will be summarized by type of health care utilisation and by treatment group.

The number of subjects with major deviations will be summarized by category of violation and by treatment group.

Adherence to the device will be summarized using descriptive statistics for the subjects randomised to dCBT-PF.

Demographic and baseline characteristics will be summarized using descriptive statistics for each treatment group and for the total number of randomised subjects. Medical history will be coded using MedDRA and summarized by system organ class and preferred term for each treatment group. Prior medications will denote medications used prior to first dose of

investigational medical device independent and stopped at latest at randomization. Concomitant therapy will denote medications started prior to but continuing after randomization or medications with a start date at or after the randomization date. Prior and concomitant therapy will be summarized separately by Anatomical Therapeutic Chemical levels 2 and 4.

Subgroup analyses of the primary and key secondary endpoints will be made to assess consistency of the intervention effect across at least the following subgroups:

[figure not shown]
- Age group: $<65 \text{ vs} \ge 65 \text{ years}$
- Sex: female vs male
- Baseline disease severity (GAD-7 score at baseline: 5-9, 10-14, ≥15)

If the number of subjects is too small (less than 10%) within a subgroup, then the subgroup categories may be redefined prior to data analysis. Further details on the statistical analysis will be provided in a statistical analysis plan.

Answers to functionality interview of the DTx will be evaluated using qualitative methods and will be reported separately.

9.4. Sample Size Re-estimation

No sample size re-estimation will be made as a result of the data collected in the pilot part of the investigation.

10. Supporting Documentation and Operational Considerations

10.1. Appendix 1: Regulatory, Ethical, and Clinical investigation Oversight Considerations

10.1.1. Regulatory and Ethical Considerations

This clinical investigation will be conducted in accordance with the CIP and with the following:

- Consensus ethical principles derived from international guidelines including the Declaration of Helsinki and Council for International Organizations of Medical Sciences international ethical guidelines.
- Applicable FDA, ISO and GCP guidelines.
- Applicable laws and regulations.

The CIP, substantial amendments, ICF and other relevant documents (e.g., subject facing material and advertisements) will be submitted to an IRB and reviewed and approved by the IRB before the clinical investigation is initiated.

Any amendments to the CIP will require IRB approval before implementation of changes except for changes necessary to eliminate an immediate hazard to subjects.

The investigator will be responsible for the following:

- o Providing written summaries of the status of the clinical investigation to the IRB annually or more frequently in accordance with the requirements, policies, and procedures established by the IRB.
- Notifying the IRB of SAEs or other significant safety findings as required by IRB procedures.
- o Providing oversight of the conduct of the clinical investigation at the site and adherence to requirements of 21 CFR (part 812), ISO 14155, medical device regulation (MDR), the IRB and all other applicable local regulations.

10.1.2. Financial Disclosure

Investigators and sub-investigators will provide the sponsor with sufficient, accurate financial information as requested to allow the sponsor to submit complete and accurate financial certification or disclosure statements to the appropriate regulatory authorities. Investigators are responsible for providing information on financial interests during the clinical investigation and for 1 year after completion of the clinical investigation.

10.1.3. Informed Consent Process

The investigator or his/her representative will via the telehealth system explain the nature of the clinical investigation, including the risks and benefits, to the subject and answer all questions regarding the clinical investigation.

Subjects must be informed that their participation is voluntary. Subjects will be required to sign a statement of informed consent that meets the requirements of 21 CFR 812, local regulations, ISO

14155, MDR, data privacy, and data protection requirements, where applicable, and the IRB or site.

Subjects must be reconsented, as applicable, to the most current version of the ICF(s) during their participation in the clinical investigation.

A copy of the signed ICF(s) must be provided to the subject.

10.1.4. Data Protection

Subjects will be assigned a unique identifier by the sponsor. Any subject records or datasets that are transferred to the sponsor will contain the identifier only; subject names or any information which would make the subject identifiable will not be transferred.

The subject must be informed that his/her personal clinical investigation-related data will be used by the sponsor in accordance with local data protection law. The level of disclosure must also be explained to the subject who will be required to give consent for their data to be used as described in the informed consent.

The subject must be informed that his/her medical records may be directly examined by Clinical Quality Assurance auditors or other authorized personnel appointed by the sponsor, by appropriate IRB members, and by inspectors from regulatory authorities.

10.1.5. Committees Structure

10.1.5.1. Data Monitoring Committee

An independent data monitoring committee (DMC) will be established to provide oversight of the pivotal phase of the investigation.

The functions and responsibilities of the DMC will be described in a DMC charter.

Throughout the duration of the investigation, the DMC will evaluate all SADEs on an ongoing basis. In addition, the DMC will meet at least once during the investigation (timepoint(s) to be defined in the charter) to review safety and efficacy data to oversee the safety of the investigation, subjects, and the scientific validity and integrity of data collected as part of the investigation.

The DMC will provide appropriate written recommendations to the Sponsor regarding investigation continuation and/or investigational plan modifications.

Any safety related DMC recommendations that may result in investigational plan changes or to the management of subjects in the investigation will be reported to the IRB.

10.1.6. Dissemination of Clinical Investigation Data

Information about the clinical investigation will be posted on the US National Institutes of Health's website www.clinicaltrials.gov prior to the first subject entering the pivotal phase of the clinical investigation.

[figure not shown]
10.1.7. Data Quality Assurance

All subject data relating to the clinical investigation will be collected at the virtual site in one central clinical system. Data will be entered by the subjects in an electronic patient reported

outcome (ePRO) system or by the site staff. An overview of the data flow is provided in Figure 1.

- The clinical system will have the following functionalities:
 - o Pre-screening system
 - o Telehealth system
 - o eConsent
 - o ePRO system
 - o Randomisation (IRT)
 - o Site assessments EDC system
 - Source documentation
 - Information on use of the dCBT-PF will be collected in the dCBT-PF database and will be transferred to the clinical investigation database
 - Medical records (CT report) confirming the PF diagnosis will uploaded in the source documentation system (not applicable for the pilot part of the investigation).

Figure 1: Data flow

- The investigator must permit clinical investigation-related monitoring, audits, IRB review, and regulatory agency inspections.
- Monitoring details describing strategy, including definition of critical data items and processes (e.g., risk-based initiatives in operations and quality such as risk management

and mitigation strategies and analytical risk-based monitoring), methods, responsibilities, and requirements, including handling of noncompliance issues and monitoring techniques (central, remote, or on-site monitoring) are provided in the monitoring plan.

- The sponsor or designee is responsible for the data management of this clinical investigation, including quality checking of the data.
- The sponsor assumes accountability for actions delegated to other individuals (e.g., contract research organizations).
- Records and documents, including signed ICFs, pertaining to the conduct of this clinical investigation must be retained by the investigator for 10 years after completion of the clinical investigation or after the last device is sold, unless local regulations or institutional policies require a longer retention period. No records may be destroyed during the retention period without the written approval of the sponsor. No records may be transferred to another location or party without written notification to the sponsor.

